1.3. Risk/Benefit Section

1.3.1. Known Benefits

The clinical benefits of vaccination with Ad26.RSV.preF have yet to be established. For the subjects in this study the vaccine may have no direct benefit.

1.3.2. Potential Benefits

Results from clinical studies with Ad26.RSV.preF may be useful in developing a new vaccine to prevent RSV infection. The vaccination may provide some protection against subsequent RSV infection in adults participating in the study who have been screened for susceptibility to RSV infection.

1.3.3. Known Risks

All vaccines have the potential to cause adverse experiences. To date, limited clinical data with Ad26.RSV.preF are available from the Phase 1 VAC18193RSV1003 study in elderly subjects aged ≥ 60 years in stable health. Safety data from an unblinded interim analysis at 28 days post-Dose 1 from all subjects who received Ad26.RSV.preF (5×10^{10} vp or 1×10^{11} vp) or placebo did not reveal any safety concerns.

No specific safety concerns were identified based on the currently available clinical data.

1.3.4. Potential Risks

The following potential risks for Ad26.RSV.preF will be monitored during the study.

Risks Related to Vaccines

Subjects may exhibit local signs and symptoms associated with vaccination, including erythema, swelling/induration, and pain/tenderness. These local reactions will be monitored, but are generally short-term and do not require treatment.

Subjects may exhibit general signs and symptoms associated with administration of a vaccine, or vaccination with placebo, including fatigue, headache, myalgia, arthralgia, chills and nausea. These side effects will be monitored, but are generally short-term and do not require treatment.

Subjects may have an allergic reaction to the vaccination. An allergic reaction may cause a rash, hives or even difficulty breathing. Severe reactions, including anaphylaxis, are rare but can occur with any vaccine. Medications will be available in the clinic to treat serious allergic reactions promptly. Subjects with a known allergy, or history of anaphylaxis or other serious adverse reactions to vaccines or vaccine components (including any of the constituents of the study vaccine) will be excluded from the study. The study site should have medical treatment available in case of severe allergic reactions following vaccine administration.

Risks Related to Adenoviral-vectored Vaccines

Safety data available from 10 completed clinical studies in adults with other Ad26-vectored vaccine candidates, in which Ad26 with different inserts has been evaluated at dose levels ranging from 1×10^9 vp to 1×10^{11} vp, indicate that no safety concerns would be anticipated from vaccination with Ad26.RSV.preF at doses of 5×10^{10} vp and 1×10^{11} vp.

Local AEs (moderate injection site pain and tenderness, and moderate to severe redness at the injection site) and systemic AEs (headache, chills, joint pain, muscle pain, tiredness/generally not feeling well/fatigue and fever) have been reported after vaccination with Ad26-vectored vaccines. In a few subjects, transient laboratory abnormalities have been seen, including changes in neutrophils (neutropenia/neutrophil count decreased). Laboratory changes including decreased hemoglobin, decreased platelets, and moderate elevations in liver transaminases were observed that were not associated with any clinical findings and appear to be transient based on no reported persistent abnormalities in any of the subjects.

For further details on the safety profiles of other Ad26-vectored vaccine candidates, see the Ad26.RSV.preF Investigator's Brochure.¹

Risks from Collection of Nasal Wash Samples/Nasopharyngeal Swabs

Collection of nasal wash samples or nasopharyngeal swabs may cause a nosebleed.

Risks from Blood Draws

Blood drawing may cause pain/tenderness, bruising, bleeding, lightheadedness, dizziness, vasovagal response, and, rarely, infection at the site where the blood is taken.

Pregnancy and Birth Control

The effect of the study vaccine on a fetus or nursing baby is unknown so women of childbearing potential are required to agree to practice effective birth control measures for sexual intercourse from signing the informed consent form (ICF) until at least 4 months after vaccination (see Section 4.1). Use of hormonal contraception should start at least 28 days before vaccination. Women who are pregnant or breast-feeding, or are planning to become pregnant while enrolled in the study until 6 months after study vaccination, will be excluded from the study. Men having sexual intercourse with women or men are required to agree to use effective contraception for sexual intercourse starting from entry to the quarantine Unit and continuing until 3 months after the date of viral challenge (see Section 4.3).

Subjects with Immuno-suppression/Reduced Immune Response

Limited evidence indicates that inactivated vaccines (or non-replicating viral vaccines) generally have the same safety profile in immunocompromised patients as in immunocompetent individuals. However, the magnitude, breadth, and persistence of the immune response to vaccination may be reduced or absent in immunocompromised persons. Subjects with abnormal function of the immune system will be excluded from the study.

Concomitant Vaccination

Concomitant vaccination might have an influence on both safety profile and immunogenicity of Ad26.RSV.preF. Likewise, Ad26.RSV.preF might have an influence on both safety profile and immunogenicity of any concomitant vaccination. As a result, vaccination with live attenuated vaccines within 28 days of a study vaccination (ie, before and after) is prohibited. Other vaccines (eg, influenza, tetanus, hepatitis A, hepatitis B, rabies) should be given at least 14 days before (or at least 14 days after) administration of study vaccine. If a vaccine is indicated in a post-exposure setting (eg, rabies or tetanus), it must take priority over the study vaccine.

Risks Associated with the Human Challenge Model

Healthy adult subjects will be recruited as they are best suited to tolerate inoculation of the virus.

Severe complications tend to occur almost exclusively in infants, the elderly, and persons of any age with chronic co-morbidities or who are significantly immune-compromised. Qualified doctors and nurses in the quarantine Unit will manage any symptoms.

As a consequence of the RSV-A Memphis 37b inoculation, AEs (serious or non-serious) related to RSV infection commonly occur. These anticipated AEs are related to, but not limited to, rhinitis, rhinorrhea, nasal congestion, sneezing, nasopharyngitis, ear ache, malaise (tiredness), cough, shortness of breath, muscle and/or joint pain, headache, fever, nasal blood spotting, and

upper respiratory tract infection. In addition, laboratory abnormalities related to RSV viral infection may occur such as, but not limited to, hematologic changes (increases in white blood cell [WBC] count and changes in differential values) and increased levels of inflammatory markers (eg. C-reactive protein).

The study virus, like many viruses, can cause more substantial health issues such as myocarditis. However, the chance of this resulting in permanent changes is rare as most cases are minor and resolve without sequelae. In over 500 subjects inoculated with the study virus by hVIVO, clinical laboratory tests in 2 subjects have shown changes suggestive of myocardial inflammation: both cases returned to normal without treatment and were not associated with specific symptoms or ECG changes.

It is unlikely that subjects will transmit RSV virus to their close contacts after they have been released from the quarantine Unit. After infection with RSV, infectious virus will be present in the subject's nose for several days, but it is not expected to be present in the subject's nose at the time of discharge from the Unit. This is because the usual duration of time that RSV remains infective in adults is several days shorter than the time they will spend in the Unit in isolation.⁹

All subjects will stay in the quarantine Unit from 1 or 2 days prior to RSV inoculation until 12 days after challenge. Nasopharyngeal swabs will be tested for the presence of virus prior to discharge using rapid virus antigen test (RVAT). Subjects will only be discharged when no detectable virus is present (negative RVAT). If symptoms are present, but no virus is detected (negative RVAT), discharge will be at the investigator's discretion. If appropriate, subjects may reside in quarantine for an additional night or longer before discharge.

To reduce the risk of passing RSV on to others, the subject will be advised to avoid contact with the following vulnerable groups of people for two weeks after they leave the quarantine Unit:

- any person with any known immunodeficiency
- any person receiving immunosuppressant medications
- any person undergoing or soon to undergo cancer chemotherapy
- any person who has congestive heart failure or is in frail health
- any person who has a diagnosis of emphysema or chronic obstructive pulmonary disease (COPD), is elderly residing in a nursing home, or has severe lung disease
- any person who has received a transplant (bone marrow or solid organ)
- children below the age of 1 year
- elderly persons (aged 75 years or older).

Unknown Risks

There may be other serious risks that are not known.

1.3.5. Overall Benefit/Risk Assessment

Based on the available data and proposed safety measures, the overall benefit/risk assessment for this clinical study is considered acceptable for the following reasons:

- The dose of Ad26.RSV.preF to be used in this study will be 1×10^{11} vp. There were no safety concerns with this dose in study VAC18193RSV1003 in elderly subjects aged ≥ 60 years in stable health. This dose was found to be safe and well-tolerated in other Ad26-vectored vaccines against HIV and Ebola.
- The study will be paused prior to challenge if one or more subjects experience any vaccine-related SAEs, or two or more subjects experience severe AEs considered to be at least possibly related to Ad26.RSV.preF after discussion between sponsor and investigator (see Section 17.9.2). In these situations, the pausing rules will apply (see Section 11.10).
- The study will be terminated if one or more subjects experience any severe or clinically significant illness from RSV challenge, after discussion with the investigator, hVIVO, and the sponsor's study-responsible physician (SRP) (see Section 17.9.2).
- Several safety measures have been proposed to minimize potential risk to subjects, including:
 - Only subjects who meet all of the inclusion criteria and none of the exclusion criteria (as specified in the protocol) will be allowed to participate in this study. The selection criteria include adequate provisions to minimize the risk and protect the well-being of subjects in the study.
 - Utilization of sentinel subjects (see Section 3.1).
 - Utilization of withdrawal criteria (see Section 10.2).
 - Close monitoring of subjects throughout the study as described in Section 9.

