11.10. Study Vaccination Pausing Rules

The investigator and the SRP will monitor the study vaccination pausing rules. If study vaccination is considered to raise significant safety concerns, further vaccination of subjects will be suspended until DRC review is carried out and subsequent communication between the sponsor and the investigators takes place.

The occurrence of any of the following events will lead to suspension of further study vaccination, and trigger a meeting of the DRC to discuss study suspension, adaptation or discontinuation of further vaccination:

1. One or more subject experience an SAE or other potentially life-threatening (Grade 4) event that is determined to be related to study vaccine; *OR*
2. One or more subjects experience anaphylaxis clearly not attributable to other causes than vaccination with study vaccine; *OR*
3. Two or more subjects experience a Grade 3 or 4 unsolicited AE of the same type, determined to be related to study vaccine, that persists for 72 hours or longer; *OR*
4. Two or more subjects experience a Grade 3 or 4 solicited systemic AE of the same type, determined to be related to study vaccine, that persists for 72 hours or longer; *OR*
5. Two or more subjects experience a persistent (upon repeat testing) Grade 3 or 4 laboratory abnormality related to the same laboratory parameter and considered related to study vaccine, that persists for 72 hours or longer; *OR*
6. Death of any subject, regardless of causality.

If any of the above specific pausing rules are met, the DRC will make recommendations regarding the continuation of the study to the sponsor. Study suspensions or terminations will occur within 5 working days after the decision is made, unless local regulations specify a shorter timeframe. Local regulatory authorities including IECs/IRBs will be informed within the appropriate regulatory-mandated timeframes. A study may be resumed only upon approval of a substantial amendment to the initial study application by the local regulatory authorities and IECs/IRBs. The sponsor will communicate conclusions regarding study continuation to the investigators, the IECs/IRBs and the national regulatory authorities as appropriate.

The investigator may ask for a review meeting to be held for any single event or combination of multiple events which, in his/her professional opinion, jeopardize the safety of the subjects or the reliability of the data.

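### Protocol 1.3.5 promises a pause before challenge, but 11.10, which it relies on, automatically suspends only further vaccination and has narrower two-subject triggers

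*Protocol*

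**What the plan says.** Protocol 1.3.5 lists its reasons for accepting the benefit/risk. One of them reads: "The study will be paused prior to challenge if one or more subjects experience any vaccine-related SAEs". The same sentence adds a second condition: "two or more subjects experience severe AEs considered to be at least possibly related to Ad26.RSV.preF after discussion between sponsor and investigator". It cites 17.9.2 for the pause and then says that the 11.10 pausing rules apply in these situations.

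Protocol 11.10 assigns the monitoring: "The investigator and the SRP will monitor the study vaccination pausing rules". On the automatic action it says: "The occurrence of any of the following events will lead to suspension of further study vaccination". The same events also "trigger a meeting of the DRC to discuss study suspension, adaptation or discontinuation of further vaccination". The triggers are:

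- Rule 1, one subject: "One or more subject experience an SAE or other potentially life-threatening (Grade 4) event that is determined to be related to study vaccine".
- Rules 2 and 6: anaphylaxis attributable to the vaccine, and any death.
- Rule 3, two subjects: Grade 3 or 4 unsolicited events of one type, vaccine-related, lasting at least 72 hours.
- Rule 4: "Two or more subjects experience a Grade 3 or 4 solicited systemic AE of the same type, determined to be related to study vaccine", with the same 72-hour condition.
- Rule 5: repeat-confirmed Grade 3 or 4 laboratory abnormalities in two subjects, "related to the same laboratory parameter and considered related to study vaccine, that persists for 72 hours or longer".

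Protocol 17.9.2 covers the sponsor's right to terminate, site closure, and termination for illness caused by the challenge. It has no pause for vaccine-related events.

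The bars to challenge in Protocol 4.3, 5 and 10.2, and the Day 0 status check in 9.1.5.1, work subject by subject. Section 5 says that a subject with an SAE before admission is not challenged and is replaced. It does not mention the 1.3.5 pause.

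**The concern.** The design has two exposures per subject: a single vaccine dose and then, 24 to 90 days later, intranasal inoculation with RSV. If a vaccine-related safety signal appears after a cohort has been dosed, the exposure still ahead of that cohort is the inoculation. A rule that stops only vaccination does not touch it, and in the last cohort there may be no doses left to stop.

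Section 1.3.5 recognises this and promises a pause before challenge. The rules that staff are told to watch do not carry that promise. A team working from 11.10 alone could suspend vaccination, call the DRC, replace the affected subject as Section 5 directs, and go on to challenge the rest while the review is open. What is at stake is subject safety and whether a safeguard used to justify the study is in place operationally. The primary analysis and sample size are not affected.

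**Working it through.** The plan states no figure on this point to reproduce. The check compares the sections and then counts who is affected.

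**1. Action.** Section 1.3.5 pauses the study before challenge. Section 11.10 automatically suspends further vaccination; study suspension is a topic for the DRC meeting and not an automatic result. The investigator's discretionary power in 11.10 to act before a rule is met also concerns vaccination only. The investigator may ask for a review meeting, but that is not a hold on challenge.

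**2. Triggers.**

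- Vaccine-related SAE in one subject: in both sections. The trigger agrees and the action differs.
- Single related Grade 4 event, anaphylaxis, any death: named only in 11.10, which is broader here.
- Severe related AEs in two subjects: 1.3.5 requires sponsor-investigator discussion but no common event type and no minimum duration. Rules 3 to 5 of 11.10 require the same type or the same laboratory parameter and at least 72 hours, and omit solicited local events.

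Two examples meet the 1.3.5 event description and no 11.10 rule: two subjects with different related Grade 3 AEs, and two subjects with the same related Grade 3 AE lasting 48 hours (neither event being serious). The wording on attribution also differs (possibly related versus related), but 12.1.2 uses a two-level scale in which a reasonable possibility counts as related, so I give that no weight.

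**3. Who is affected in cohort 1.** Inputs: 26 vaccinated and 22 challenged (Protocol 3.1); 1:1 randomization in permuted blocks (Protocol 5). Suppose one subject has a vaccine-related SAE after the whole cohort has been dosed.

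- Others with no subject-level bar from that event: 26 − 1 = 25.
- Doses left in that cohort to suspend: 0.
- Active recipients among the 25, if the affected subject was on active: 26/2 − 1 = about 12. The other 13 or so received saline. The block size is not stated, so the split is approximate.
- Challenge places still to fill: 22.

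**4. Time available.** Solicited events are collected to Day 7 after vaccination and challenge is at Day 24 at the earliest: 24 − 7 = 17 days. That runs from the end of collection, not from detection. The Day 7 visit has a window of ±2 days, so a review on Day 9 leaves 24 − 9 = 15 days. If that visit falls before the diary period ends, the diary is handed in only at Unit admission. Anything first found at admission leaves 1 to 2 days, which is shorter than the 72 hours in rules 3 to 5 and may be shorter than the 5 working days that 11.10 allows for putting a suspension decision into effect. The mismatch therefore matters mainly for events found late.

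**The case against.** The strongest reply is that the pause already exists. Section 1.3.5 is current protocol text and can be read as cumulative with 11.10: the first pauses the study, the second adds the vaccination hold and the DRC review. Nothing in 11.10 permits challenge during a 1.3.5 pause. For a vaccine-related SAE the triggers agree, SAEs must reach the sponsor within 24 hours (12.3.2), and the DRC advises on continuation of the study as a whole (11.9). A broad trigger with discussion, alongside narrow automatic ones, could be a deliberate two-tier scheme.

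Much of this stands. A reader might infer that nothing would stop challenge after a vaccine-related SAE. The documents do not support that: 1.3.5 can be applied directly, and the DRC can recommend suspension. Nor is 11.10 weaker throughout, as the single-subject rules show.

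The reply does not remove the conflict. Staff are told to monitor 11.10, and the hold is not there. The two-tier reading leaves the broad tier with no place in the operational rules and a reference to 17.9.2 that leads nowhere for the pause. Section 11.10 also says that stopping rules apply to the whole study because there is a single site; that sentence most naturally concerns sites, and does not extend a vaccination stop to challenge.

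A reader might also treat all 25 subjects as carrying a vaccine-related hazard. About 13 of them would have received saline. They are counted because the blind means that a hold has to cover everyone.

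**Conclusion.** The conflict is in the current text. Section 1.3.5 relies on a pause before challenge that the rules in 11.10 do not contain and that 17.9.2 does not supply, and the two-subject triggers differ in substance. It is an inconsistency in safety governance that should be corrected; it is not an absence of protection.

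The cohort 1 count assumes that the event occurs after all 26 are vaccinated and that the affected subject was on active. The documents give no event rates, so no probability can be attached. It would also go too far to conclude that the site has no working hold on challenge: the DRC charter and the sponsor's suspension procedures are cited but not available here, and may contain one.

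**What to change.** Amend the protocol in three places:

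1. In 11.10, state that when a 1.3.5 condition is met (at minimum a vaccine-related SAE, or two or more subjects with severe related AEs after sponsor-investigator discussion), viral challenge of all vaccinated subjects not yet inoculated is held until the DRC review is complete.
2. List the 1.3.5 two-subject condition in 11.10 as a trigger for that hold.
3. In 1.3.5, remove 17.9.2 as the reference for the pause and point it to 11.10.

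Two choices belong to the sponsor: whether the other 11.10 rules should also hold challenge, and whether lifting the hold needs a substantial amendment. The documents settle neither.

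The cost is amendment text, a possible short delay of a challenge cohort, and rescheduling of anyone already admitted. From the Day 28 target, the challenge window leaves 90 − 28 = 62 days. Overflow subjects waiting for the next cohort have less. Assume a full Unit, discharge on Day 12 after challenge, the next cohort entering that day and challenged one day later. With cohort 1 challenged on Day 28, they reach challenge at 28 + 12 + 1 = Day 41 after vaccination, leaving 90 − 41 = 49 days. With cohort 1 challenged on Day 24, it is 24 + 12 + 1 = Day 37, leaving 90 − 37 = 53 days. If lifting the hold did require a substantial amendment, approval could use up this slack; the documents give no approval times.

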2. OBJECTIVES, ENDPOINTS, AND HYPOTHESIS

2.1. Objectives and Endpoints

2.1.1. Objectives

Primary Objective

The primary objective is to assess a trend for the prophylactic efficacy of a single dose of 1×10^{11} vp of Ad26.RSV.preF administered intramuscularly to adults aged 18-50 years in the RSV challenge model in terms of reduction of nasal wash viral load as measured by the area under the curve (AUC) over time by quantitative reverse transcriptase-polymerase chain reaction (RT-PCR) compared to placebo.

Secondary Objectives

- To assess a trend for prophylactic efficacy of a single dose of Ad26.RSV.preF in the RSV challenge model in terms of reduction of nasal wash viral load as measured by the peak viral load of the RT-PCR compared to placebo.
- To assess the effect of a single dose of 1×10^{11} vp of Ad26.RSV.preF on viral load, as measured by RT-PCR and quantitative culture of RSV, and clinical symptoms on Day 6 and Day 7 post-challenge compared to placebo.
- To assess a trend for prophylactic efficacy of a single dose of 1×10^{11} vp of Ad26.RSV.preF in the RSV challenge model in terms of prevention of symptomatic RSV infection defined as two quantifiable RT-PCR measurements and one or more positive clinical symptoms of any grade from two different categories in the symptom scoring system (Upper Respiratory, Lower Respiratory, Systemic), or one Grade 2 symptom from any category compared to placebo.
- To assess a trend for prophylactic efficacy of a single dose of 1×10^{11} vp of Ad26.RSV.preF in the RSV challenge model in terms of prevention of symptomatic RSV infection defined as two quantifiable RT-PCR measurements and one or more positive clinical symptoms of any grade in any category from the symptom scoring system compared to placebo.
- To assess a trend for prophylactic efficacy of a single dose of 1×10^{11} vp of Ad26.RSV.preF in the RSV challenge model in terms of the weight of mucous secretions and tissue count over time compared to placebo.
- To assess the safety and tolerability of a single dose of 1×10^{11} vp of Ad26.RSV.preF administered intramuscularly.

Exploratory Objectives

- To assess a trend for prophylactic efficacy of a single dose of 1×10^{11} vp of Ad26.RSV.preF in the RSV challenge model in terms of clinical symptoms as measured by the AUC over time of symptoms collected by a graded symptom scoring system compared to placebo.
- To assess a trend for prophylactic efficacy of a single dose of 1×10^{11} vp of Ad26.RSV.preF in the RSV challenge model in terms of AUC for viral load (VL-AUC), as measured by quantitative culture of RSV from nasal wash samples, compared to placebo.
- To explore the relationship of humoral (including nasal wash samples if feasible) and cellular immunogenicity outcomes and the VL-AUC and the AUC for clinical symptoms.
- To assess a trend for prophylactic efficacy of a single dose of 1×10^{11} vp of Ad26.RSV.preF in the RSV challenge model in terms of prevention of symptomatic RSV infection defined as two quantifiable RT-PCR measurements and/or positive serological measurement of RSV infection in the context of immunization and pre-existing antibody and one or more positive clinical symptoms of any grade in any category compared to placebo.

- To assess a trend for prophylactic efficacy of a single dose of 1×10^{11} vp of Ad26.RSV.preF in the RSV challenge model in terms of respiratory parameters measured by spirometry during the study compared to placebo.
- To explore the relationships between clinical symptoms and viral load, as measured by RT-PCR and quantitative culture of RSV, in Ad26.RSV.preF subjects and placebo.
- To explore other immunologic parameters in relation to the VL-AUC by RT-PCR and AUC for clinical symptoms and occurrence of symptomatic RSV infection defined as two quantifiable RT-PCR measurements or more plus one clinical symptom of any grade.
- To explore the immune response of a single dose of 1×10^{11} vp of Ad26.RSV.preF compared to placebo.
- To explore humoral and cellular responses to challenge with RSV-A Memphis 37b in immunized and non-immunized subjects.
- To explore the relationship between immunogenicity and pre-existing Ad26 neutralizing antibody.
- To explore other potential efficacy endpoints, as defined in the statistical analysis plan (SAP), to determine the best efficacy endpoint to use in subsequent clinical studies investigating the vaccine's efficacy.

Objectives and endpoints are tabulated in [Attachment 2](#).

